9.6. Sample Collection and Handling

The actual dates and times of sample collection must be recorded in the CRF or laboratory requisition form. If blood samples are collected via an indwelling cannula, an appropriate amount (ie, 2 mL) of fluid slightly greater than the dead space volume of the lock will be removed from the cannula and discarded before each blood sample is taken. After blood sample collection, the cannula will be flushed with 10 U/mL of sodium heparin and filled to the volume equal to the dead space volume of the lock.

Refer to the [TIME AND EVENTS SCHEDULE](#) for the timing and frequency of all sample collections.

Instructions for the collection, handling, storage, and shipment of samples are found in Method for Pharmacokinetics Sample Collection, Handling and Shipping (PK) that will be provided. Collection, handling, storage, and shipment of samples must be under the specified, and where applicable, controlled temperature conditions as indicated in Method for Pharmacokinetics Sample Collection, Handling and Shipping (PK).

10. SUBJECT COMPLETION/DISCONTINUATION OF STUDY TREATMENT/ WITHDRAWAL FROM THE STUDY

10.1. Completion

A subject will be considered to have completed the study if he or she has completed all the required assessments.

10.2. Withdrawal From the Study

A subject will be automatically withdrawn from the study for any of the following reasons:

- subjects who vomit within 6 hours after study drug administration
- Lost to follow-up
- Withdrawal of consent

- Death
- Noncompliance defined as :
 - subject is not in compliance with requirements of the study, including inclusion criteria, exclusion criteria, and prohibitions and restrictions

If a subject withdraws from the study for any reason before the end of the study, end-of-treatment assessments should be obtained.

If a subject is lost to follow-up, every reasonable effort must be made by the study site personnel to contact the subject and determine the reason for discontinuation/withdrawal. The measures taken to follow up must be documented.

When a subject withdraws before completing the study, the reason for withdrawal is to be documented in the CRF and in the source document. Study drug assigned to the withdrawn subject may not be assigned to another subject. If a subject withdraws from the study before the end of the study, end-of-treatment assessments should be obtained.

If more than 2 subjects withdraw before the completion of all the assessments scheduled on Day 4 for reason other than safety, additional subjects will be enrolled to ensure at least 6 subjects complete all the assessments scheduled on Day 4.

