3. STUDY DESIGN AND RATIONALE

3.1. Overview of Study Design

This is a single center open-label, single oral dose study in healthy Japanese adult subjects. Eight subjects will be enrolled to ensure that at least 6 subjects complete the study up to Day 4. The study consists of 3 phases; a screening phase from Day -21 to Day -2, an in-patient period-phase from Day -1 to Day 4 (dosing day is Day 1), and an End of Study phase with a visit scheduled 7 to 10 days after the intake of study drug or at the time of early withdrawal.

As depicted in [Figure 1](#), eight subjects who satisfy all inclusion criteria and do not meet any exclusion criteria will receive Prezcobix at Day 1. Subjects who met the selection criteria at screening will be admitted to the investigational institute on the day before administration (Day -1). All enrolled subjects will receive a single oral dose of one Prezcobix tablet on Day 1 (there is no Day 0) within 30 minutes after start of the standardized breakfast (see [Figure 1](#)), and the breakfast should be fully ingested within 30 minutes. All subjects will remain in the investigational institute for the entire duration of the in-patient phase. Subjects will be discharged on Day 4 after the completion of all required assessments. Subjects will visit the investigational institute on the days as scheduled until the last follow-up assessment on Day 7 - Day 10. Serial blood samples for the determination of plasma concentrations for each component of Prezcobix will be collected over a period of 72 hours. Details on the timing of the dose and the PK and safety assessments are given in the [TIME AND EVENTS SCHEDULE](#).

Figure 1: Schedule Overview of the Study

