4. SUBJECT POPULATION

Screening for eligible subjects will be performed within 21 days before administration of the study drug.

Eight subjects will be enrolled to ensure that at least 6 subjects complete the study up to Day 4. If more than 2 subjects withdraw from the study before completion up to Day 4 for reasons other than safety, additional subjects will be enrolled to ensure that at least 6 subjects complete the study up to Day 4.

The inclusion and exclusion criteria for enrolling subjects in this study are described in the following 2 subsections. If there is a question about the inclusion or exclusion criteria below, the investigator should consult with the appropriate sponsor representative before enrolling a subject in the study.

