2. GENERAL ANALYSIS DEFINITIONS

2.1. Visit Windows

The evaluations are described in “Time and Events Schedule” of the protocol and the allowance are described below.

Analysis time point		Allowance	Physical Examination	Vital Signs a), b)	12-lead ECG ^{a)}	Clinical Labs ^{c)}
Screening		Day -21 to Day -2	X	X	X	X
Day -1		Within Day-1	X	X	X	X
Day 1	Predose	Within Day1 and before intake of Prezcobix	X	X	X	
	3 hr	Within Day1 and +/- 30 min.		X	X	
Day 2		Within Day 2	X	X	X	X
Day 4		Within Day 4	X	X	X	X
End-of-Study (Day 7 -10)		Within the day Day 7 -10	X	X	X	X

a) When blood samples are to be collected and 12-lead ECG and/or vital signs are to be checked at the same time point, blood samples will be collected after completion of other evaluations.

b) Vital signs include respiration rate, supine blood pressure, pulse and temperature (axillary) after more than 5 minutes rest.

c) Clinical labs include hematology, biochemistry and urinalysis. Subjects will fast for at least 10 hours prior to the blood sampling for clinical labs.

Pharmacokinetics

Analysis time point		Allowance	Pharmacokinetics
Day 1	Predose	Before intake of Prezcobix	X ^{a)}
	0 hr		
	0.5 hr	0.4 hr to 0.6 hr	X
	1 hr	0.8 hr to 1.2 hr	X
	1.5 hr	1.25 hr to <1.75 hr	X
	2 hr	1.75 hr to <2.25 hr	X
	2.5 hr	2.25 hr to <2.75 hr	X
	3 hr	2.75 hr to 3.25 hr	X ^{a)}
	4 hr	3.5 hr to <4.5 hr	X
	5 hr	4.5 hr to <5.5 hr	X
	6 hr	5.5 hr to 6.5 hr	X
	9 hr	8.0 hr to <10.0 hr	X
	12 hr	10.0 hr to <14.0 hr	X
	16 hr	14.0 hr to <18.0 hr	X
	20 hr	18.0 hr to <22.0 hr	X
Day 2	24 hr	22.0 hr to 26.0 hr	X ^{a)}
	36 hr	30.0 hr to <42.0 hr	X
Day 3	48 hr	42.0 hr to <54.0 hr	X
	60 hr	54.0 hr to <66.0 hr	X
Day 4	72 hr	66.0 hr to 78.0 hr	X ^{a)}
End-of-Study (Day 7-10)/ Early Withdrawal			X ^{a) b)}

a) When blood samples are to be collected and 12-lead ECG and/or vital signs are to be checked at the same time point, blood samples will be collected after completion of other evaluations.

b) At the end of study or early withdrawal, sample PK will be performed for early withdrawal visit only.

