- When more than half (>50%) of plasma DRV and COBI concentrations are BQL at each scheduled time point, mean, median, and minimum will be shown as 'BQL', and SD, and %CV will be shown as 'NC' (not-calculated). If all plasma DRV and COBI concentrations are BQL, maximum will also be shown as 'BQL'. If a minimum concentration is substituted to '0', 'BQL' will be presented as minimum.
- When number of plasma DRV and COBI concentrations is equal to or less than 2, only N and mean will be calculated and SD, %CV, median, minimum and maximum will be shown as 'NC' regardless of the proportion of BQL.

Subjects will be excluded from the PK analysis if their data do not allow for accurate assessment of the PK (eg. incomplete administration of the study drug; subject vomited after receiving study drug; missing information of dosing and sampling times; concentration data not sufficient for PK parameter calculation).

Based on actual sampling times, PK parameters will be estimated using a non-compartmental analysis method with WinNonlin® (Version 6.4). The detail procedure is written in "[ATTACHMENTS](#)" of this document.

The following analyses will be performed. Tables and figures:

- Descriptive statistics of plasma DRV and COBI concentrations at each sampling time point (Use the analysis time points defined in [2.1](#))
- Descriptive statistics of PK parameters of DRV and COBI
- Line plots of arithmetic mean and SD of plasma DRV and COBI concentration time profiles (Use the analysis time points defined in [2.1](#))
- Line plots of arithmetic mean and SD of plasma DRV and COBI concentration time profiles with a log scale (values of 10^{-1} , 10^0 , 10^1 , 10^2 , 10^3 , 10^4) on the Y axis (Use the analysis time points defined in [2.1](#))
- Line plots of individual plasma DRV and COBI concentration time profiles (Use all the time points observed)
- Line plots of individual plasma DRV and COBI concentration time profiles with a log scale (values of 10^{-1} , 10^0 , 10^1 , 10^2 , 10^3 , 10^4) on the Y axis (Use all the time points observed)

The following analyses will be performed. Listings:

- Listing of individual plasma DRV and COBI concentrations at each sampling time point
- Listing of PK parameters of DRV and COBI

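### Vomiting within 6 h of the only dose triggers withdrawal from the whole study, cutting three scheduled postdose safety lab sets to one; PK exclusion with continued safety follow-up would serve better

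*Protocol*

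**What the plan says.** Protocol 10.2 opens its list with "A subject will be automatically withdrawn from the study for any of the following reasons". The first entry is "subjects who vomit within 6 hours after study drug administration". The withdrawal is from the study, not only from the PK analysis. A withdrawn subject is to have end-of-treatment assessments, with no clock time or day given.

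Protocol 3.1 treats the last visit and the withdrawal visit as one, "scheduled 7 to 10 days after the intake of study drug or at the time of early withdrawal", and 9.1.4 lists a single set of procedures for both. Before that visit, 9.1.3 schedules physical examination, labs, vital signs and ECG at 24 h (Day 2) and 72 h (Day 4).

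Replacement is governed by Section 4 ("If more than 2 subjects withdraw from the study before completion up to Day 4 for reasons other than safety") and repeated in 10.2 ("If more than 2 subjects withdraw before the completion of all the assessments scheduled on Day 4 for reason other than safety"). The aim is at least 6 subjects who complete to Day 4.

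SAP 7.1 gives "subject vomited after receiving study drug" as an example of a reason to exclude a subject from the PK analysis. SAP 2.3.1 keeps every dosed subject in the safety set. In SAP 2.1 the allowance for the End-of-Study safety row is "Within the day Day 7 -10". Early withdrawal appears only in the PK table, where a note says "sample PK will be performed for early withdrawal visit only".

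**The concern.** In a multiple-dose study, withdrawing a subject can stop exposure. Here the one tablet has already been taken, so the rule protects the subject from nothing further. The PK summaries are protected separately by SAP 7.1.

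What withdrawal does end is the scheduled safety follow-up, and it ends it for a subject picked out by a postdose adverse event. Safety is the secondary objective. Vomiting late in the 6 h window can follow considerable absorption: Protocol Table 1 gives median tmax of 4.03 h for darunavir and 4.00 h for cobicistat in the previous study. The subject still counts in the adverse event denominator. Under Protocol 12.3.1, however, routine collection of non-serious events stops at that subject's last study-related procedure, which may now fall on Day 1 or 2.

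**Working it through.** **Scheduled lab sets.** Sections 9.1.2 to 9.1.4 and SAP 2.1 give screening, Day -1, Day 2, Day 4 and End of Study: 5 sets, 3 of them postdose. Protocol Table 3 agrees, with 5 hematology and 5 chemistry samples. Its total reproduces: 8×5 + 2×5 + 6×1 + 2×2 + 2×1 + 3×19 + 2×14 = 147 mL.

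**After withdrawal for vomiting.** One set remains. Because no day is fixed for it, each possible day was set against the SAP 2.1 lab windows:

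| Day drawn | SAP 2.1 postdose lab time point filled |
|---|---|
| 1 | none |
| 2 | Day 2 |
| 3 | none |
| 4 | Day 4 |
| 5-6 | none |
| 7-10 | End of Study |

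So 0 or 1 of 3 time points is filled. A draw soon after the vomiting fills none. It would also break the 10-hour fast required for labs, since dosing goes with breakfast. Waiting until Day 2 fills only Day 2. With one vomiter among 8, N in the by-time-point lab tables falls from 8 to 7 (1/8 = 12.5%) at the 2 or 3 time points lost.

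**How often.** The documents give no vomiting rate. At an assumed per-subject risk p, the chance of at least one case in 8 is 1 − (1 − p)^8:

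| Assumed p | At least 1 of 8 | At least 3 of 8 |
|---|---|---|
| 2% | 14.9% | 0.04% |
| 5% | 33.7% | 0.58% |
| 10% | 57.0% | 3.81% |

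**Why the replacement link must survive any change.** The planned precision is exp(± t × σ/√n), with σ = √ln(1 + 0.40²) = 0.3853.

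- n = 6, t = 2.015: 72.8% to 137.3%, matching the stated 73% to 137%.
- n = 5, t = 2.132: 69.3% to 144.4%.

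The second line applies if 3 of 8 vomit and nobody is added. It shows the cost of a careless fix.

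**Blood under the fix.** Two further safety sets are 2 × (8 + 2) = 20 mL more than under withdrawal, and the schedule stays within 147 mL. If the 9 PK draws after 6 h stop, 9 × 3 = 27 mL is saved and the total is at most 147 − 27 = 120 mL. An unscheduled lab set near the event would add 8 + 2 = 10 mL, giving 130 mL.

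**The case against.** The strongest objection is that the rule does have a purpose. SAP 7.1 removes a vomiter from the analysis but does not bring in a replacement. Under Section 4 and 10.2 replacement depends on withdrawal, and the target is 6 completers. Delete the bullet alone, and a vomiter who stays fills one of those 6 places while giving no usable PK data. This stands. A reader might infer that the bullet is redundant for PK; the replacement rule does not support that, and any fix must rebuild the link.

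A related point also stands. Replacement is limited to withdrawals not due to safety, and no section says on which side vomiting falls. Declaring it non-safety would sit badly with an argument that begins from an adverse event. If 3 of 8 volunteers vomit, dosing more of them deserves a tolerability review first.

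The loss is also smaller than the counts suggest:

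- A withdrawal set outside the SAP 2.1 windows is still an on-treatment evaluation under SAP 6.2, and appears in the listings and individual plots.
- Serious events spontaneously reported within 30 days are captured (12.3.1).
- Unscheduled safety samples are allowed (9.1.1).
- Clinically significant abnormalities persisting at withdrawal are followed (9.5).

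All of this is correct, but none of it schedules a Day 4 or Day 7-10 assessment, and 9.5 covers only abnormalities already present at withdrawal.

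Finally, the withdrawal visit can place a full assessment close to the event, whereas the next scheduled labs and physical examination are at 24 h. The fix should allow for that. The retained dose in a vomiter is unknown, so later labs are harder to interpret; that lowers their value without removing it.

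**Conclusion.** The point holds, at modest size. For each subject who vomits within 6 h, scheduled postdose lab sets fall from 3 to 1, filling 0 or 1 of the 3 SAP 2.1 time points. Routine adverse event collection can end on Day 1 or 2 while the subject remains in the Safety Analysis Set. The counts rest only on the schedule and hold whichever day the withdrawal visit takes place. How often this would happen rests on assumed vomiting rates.

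Two stronger readings are not supported. A reader might infer that the primary PK result is biased or imprecise as planned. SAP 7.1 handles vomiters in the analysis, and the 69% to 144% interval arises only if vomiters are not replaced, which the documents neither state nor rule out. A reader might also infer that the vomiter's safety data disappear. They do not: what goes is the scheduled later follow-up and some entries in descriptive tables, in a study with no hypothesis test.

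The missing early-withdrawal row in the SAP 2.1 safety table is a separate, minor matter that affects any withdrawal.

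**What to change.** 1. In Protocol 10.2, replace the vomiting bullet with: *A subject who vomits within 6 hours after dosing is not evaluable for PK and, if consenting, stays on the scheduled safety assessments through Day 7-10, with an unscheduled safety assessment near the event if clinically indicated; further PK sampling is optional.*
2. In the synopsis, Section 4 and 10.2, add to the replacement rule: *A subject not evaluable for PK because of vomiting does not count toward the 6 completers; if fewer than 6 PK-evaluable completers remain, additional subjects are enrolled after the sponsor and investigator review tolerability.* This keeps the precision target without labelling vomiting as a non-safety reason.

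The cost is protocol wording, with no new type of procedure; subjects are already due to stay in the unit to Day 4. Each vomiter has two more assessment sets and about 20 mL more safety blood than under withdrawal, within the planned 147 mL. If an unscheduled lab set is drawn, stopping later PK samples keeps the total below that figure. Extra subjects may be needed if more than 2 are lost. An early-withdrawal row in the SAP 2.1 safety table is optional.

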11. STATISTICAL METHODS

No formal hypothesis testing will be conducted. Data will be summarized using descriptive statistics. Continuous variables will be summarized using the number of observations, mean, SD, coefficient of variation, median, and range as appropriate. Categorical values will be summarized using the number of observations and percentages as appropriate.

11.1. Subject Information

For all subjects who receive at least one dose of study drug descriptive statistics will be provided. All demographic (eg, age, height, weight, BMI) and other initial subject characteristics (eg, medical history, physical examination) will be tabulated and analyzed descriptively.

11.2. Sample Size Determination

Eight subjects will be enrolled in the study to ensure that at least 6 subjects complete the study assessments up to Day 4. Based on a previous study, TMC114IFD1003, the maximum observed value of between subject coefficient of variation (CV) for C_{max} , AUC_{last} and AUC_{∞} for DRV and COBI after intake of DRV/COBI as an FDC tablet under fed conditions were 35% for DRV and 44 % for COBI in healthy nonJapanese adult subjects. Using an estimate of approximately 40% for between subject CV and a sample size of 6 subjects, the true mean C_{max} , AUC_{last} and AUC_{∞} for each component of DRV/COBI are estimated to be within 73% to 137% of the observed geometric means with 90% confidence.

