This is a single center open-label, single oral dose study in healthy Japanese adult subjects. The study consists of 3 phases; a screening phase from Day -21 to Day -2, an in-patient phase from Day -1 to Day 4 (dosing day is Day 1), and a follow-up assessment phase scheduled 7 to 10 days after the intake of the study drug or at the time of early withdrawal.

SUBJECT POPULATION

Eight subjects will be enrolled to ensure that at least 6 subjects complete the study up to Day 4. If more than 2 subjects withdraw from the study before completion up to Day 4 for reasons other than safety, additional subjects will be enrolled to ensure that at least 6 subjects complete the study up to Day 4.

Main Criteria for Inclusion

Healthy Japanese men and women between 20 and 55 years of age, inclusive; body mass index (BMI) between 18.0 and 30.0 kg/m², inclusive; and body weight not less than 50 kg.

DOSAGE AND ADMINISTRATION

One Prezcobix tablet will be taken in the morning on Day 1. The study drug will be taken orally with 240 mL of noncarbonated water within 30 minutes after start of the standardized breakfast, and the breakfast should be fully ingested within 30 minutes. The study drug must be swallowed whole, not chewed, divided, dissolved or crushed.

PHARMACOKINETIC EVALUATIONS

Venous blood will be collected for the determination of plasma concentrations for each component of DRV/COBI at the following time points;

- Predose, 0.5, 1, 1.5, 2, 2.5, 3, 4, 5, 6, 9, 12, 16, 20, 24, 36, 48, 60, 72 hours postdose and early withdrawal visit

Based on the individual plasma concentration-time data, using the actual sampling times, the following PK parameters will be estimated by noncompartmental analysis. Additional PK parameters may be estimated as well.

PK parameters for DRV and COBI: C_{\max} , C_{last} , t_{\max} , AUC_{last} , AUC_{∞} , λ_z , $t_{1/2,\text{term}}$

SAFETY EVALUATIONS

Safety will be evaluated throughout the study. Following evaluations will be performed according to the TIME AND EVENTS SCHEDULE.

- Adverse Events (AEs)
- Clinical Laboratory Tests
 - - Hematology Panel
 - - Biochemistry Panel
 - - Urinalysis
- 12-lead Electrocardiogram (ECG)
- Vital Signs (blood pressure, pulse, temperature [axillary], respiration rate)
- Physical Examination

Any clinically significant abnormalities persisting at the end of the study will be followed by the investigator until resolution or until reaching a clinically stable endpoint.

STATISTICAL METHODS

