Sample Size Determination

Eight subjects will be enrolled in the study to ensure that at least 6 subjects complete the study assessments up to Day 4. Based on a previous study, TMC114FD1003, the maximum observed value of between subject coefficient of variation (CV) for C_{\max} , AUC_{last} and AUC_{∞} for DRV and COBI after intake of DRV/COBI as an FDC tablet under fed conditions were 35% for DRV and 44% for COBI in healthy nonJapanese adult subjects. Using an estimate of approximately 40% for between subject CV and a

sample size of 6 subjects, the true mean C_{\max} , AUC_{last} and AUC_{∞} for each component of DRV/COBI are estimated to be within 73% to 137% of the observed geometric means with 90% confidence.

Pharmacokinetics

All subjects receiving the study drug and having at least one plasma concentration data after administration will be included in the pharmacokinetic analysis. Plasma concentration data will be tabulated for each component of DRV/COBI. Individual and mean concentration time profiles for each analyte will be visually presented on a linear and logarithmic scale. PK parameters for each analyte will be calculated using data of all the subjects whose concentration-time profiles allow for accurate calculation of PK parameters. The descriptive statistics (eg, number of collected data, mean, standard deviation, median, minimum, maximum, CV and geometric means) of plasma concentrations of each analyte at each time point will be reported. Individual and descriptive statistics of PK parameters of each analyte will be tabulated.

Safety

All subjects who received the study drug will be included in the safety and tolerability analysis. Baseline for all laboratory evaluations, vital signs and ECG will be defined as the last evaluation done before the study drug administration. Safety will be evaluated by examining frequency, severity and type of AEs, and changes in clinical laboratory test values (hematology, biochemistry and urinalysis), physical examination results, vital signs and ECG measurements. Safety data will be summarized using descriptive statistics and frequency tables.

TIME AND EVENTS SCHEDULE

Phase	Screening	In-patient period														End-of-Study							
Study day	Days -21 to -2	Day -1	Day 1												Day 2	Day 3	Day 4	End of Study (Day 7 – 10) or Early Withdrawal					
Time			0 h	0.5 h	1 h	1.5 h	2 h	2.5 h	3 h	4 h	5 h	6 h	9 h	12 h	16 h	20 h	24 h	36 h	48 h	60 h	72 h		
Informed consent (ICF)	X																						

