11.3. Pharmacokinetic Analyses

All subjects receiving the study drug and having at least one plasma concentration data after administration will be included in the pharmacokinetic analysis. Plasma concentration data will be tabulated for each component of DRV/COBI. Individual and mean plasma DRV/COBI concentration and concentration time profiles for each analyte will be visually presented on a linear and logarithmic scale. PK parameters for each analyte will be calculated using the data of all the subjects whose concentration-time profiles allow accurate calculation of PK parameters.

The descriptive statistics (eg, number of collected data, mean, standard deviation, median, minimum, maximum, CV, geometric means and 90% confidence intervals) of plasma concentrations of each analyte at each time point will be reported. Individual and descriptive statistics of PK parameters of each analyte will be tabulated.

PK parameters will be estimated using a noncompartmental analysis method with Phoenix WinNonlin® (Version 6.4).

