1.4. Sample Size Justification

Eight subjects will be enrolled in the study to ensure that at least 6 subjects complete the study assessments up to Day 4. Based on a previous study, TMC114IFD1003, the maximum observed value of between subject coefficient of variation (CV) for C_{max} , AUC_{last} and AUC_{∞} for DRV and COBI after intake of DRV and COBI as a Fixed-dose combination (FDC) tablet under fed conditions were 35% for DRV and 44% for COBI in healthy non Japanese adult subjects. Using an estimate of approximately 40% for between subject CV and a sample size of 6 subjects, the true mean C_{max} , AUC_{last} and AUC_{∞} for each component of DRV and COBI are estimated to be within 73% to 137% of the observed geometric means with 90% confidence.

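### Is one precision range of 73% to 137% misleading for darunavir and cobicistat, and does the plan promise six completers that it cannot guarantee?

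*Protocol*

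**What the plan says.** The sample size paragraph appears in Protocol 11.2, in the synopsis and in SAP 1.4. It takes from an earlier study in non-Japanese volunteers the largest CVs seen across Cmax, AUClast and AUC-infinity, which "were 35% for DRV and 44% for COBI in healthy non Japanese adult subjects". It then plans on one value, "Using an estimate of approximately 40% for between subject CV and a sample size of 6 subjects", and concludes that the true means of all three parameters, for each component, "are estimated to be within 73% to 137% of the observed geometric means with 90% confidence".

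On numbers, the synopsis and Protocol 11.2 say: "Eight subjects will be enrolled in the study to ensure that at least 6 subjects complete the study assessments up to Day 4". The synopsis (Subject Population) and Protocol 3.1 and 4 say nearly the same: "Eight subjects will be enrolled to ensure that at least 6 subjects complete the study up to Day 4". The replacement rule in Protocol 4 begins "If more than 2 subjects withdraw from the study before completion up to Day 4 for reasons other than safety", and only then are more subjects enrolled. Protocol 10.2 repeats the trigger: "If more than 2 subjects withdraw before the completion of all the assessments scheduled on Day 4 for reason other than safety".

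Who contributes to each parameter is set elsewhere. Protocol 11.3 calculates parameters "using the data of all the subjects whose concentration-time profiles allow accurate calculation of PK parameters". SAP 2.3.2 defines the PK set by one postdose concentration. SAP 7.1 adds criteria for the terminal slope and for extrapolation, and excludes subjects whose data do not support an accurate PK assessment.

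**The concern.** Two things catch the eye.

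- **One CV for two analytes.** The planning CV of 40% is lower than the 44% that the same paragraph reports for COBI, and no reason is given. The paragraph is the only quantitative basis for the sample size, and PK is the primary objective. If the range were materially too narrow for COBI, readers would expect more precision than six subjects can give.
- **A promise that the rule does not keep.** Enrolling eight is said to secure six completers, yet replacement starts only after more than two withdrawals for reasons other than safety. Some combinations of three withdrawals leave five subjects and start nothing. Nor does completing Day 4 guarantee an evaluable AUC-infinity, so the n behind a parameter could be lower still.

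At stake is whether the stated precision can be trusted and whether enrolment or the replacement rule needs to change.

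**Working it through.** **Inputs.** CVs of 35%, 40% and 44%, n=6 and 90% confidence come from Protocol 11.2. Eight enrolled and the replacement trigger come from Protocol 4 and 10.2.

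**Formula.** For a log-normal parameter, the log-scale SD is σ = √ln(1 + CV²). The 90% limits relative to the geometric mean are exp(±h), with h = t(0.95, n−1) × σ / √n.

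**The plan's own figure.** CV 0.40 gives σ = √ln(1.16) = 0.3853. With t = 2.0150 on 5 df, h = 2.0150 × 0.3853 / √6 = 0.3169. The limits are 72.84% and 137.29%, which round to the stated 73% and 137%.

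**The cited maxima, and other n.** The t quantiles are 2.1318 (n=5), 2.0150 (n=6), 1.9432 (n=7) and 1.8946 (n=8).

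| n | CV 35% (σ 0.3399) | CV 40% (σ 0.3853) | CV 44% (σ 0.4207) |
|---|---|---|---|
| 5 | 72.32% to 138.28% | 69.26% to 144.38% | 66.96% to 149.34% |
| 6 | 75.61% to 132.27% | 72.84% to 137.29% | 70.75% to 141.35% |
| 7 | 77.91% to 128.36% | 75.36% to 132.70% | 73.42% to 136.20% |
| 8 | 79.64% to 125.57% | 77.26% to 129.44% | 75.44% to 132.55% |

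At n=6:

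- For DRV the stated range is conservative, by about 3 points at the lower limit and 5 at the upper.
- For the most variable COBI parameter it is optimistic, by about 2 and 4 points.
- The 44% is a maximum over three parameters. Any COBI parameter with a CV of 40% or less meets the stated range.
- The planning value is close to the midpoint of the two maxima: (35 + 44)/2 = 39.5%.

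**Size against sampling noise.** The reported interval will use the observed SD, not 40%. With n=6 (5 df), the ratio of sample to true log-scale SD lies in 90% of samples between √(1.1455/5) = 0.479 and √(11.0705/5) = 1.488. Multiplying h = 0.3169 by these gives 0.152 and 0.472, that is, intervals from 85.9% to 116.4% up to 62.4% to 160.3%. A shift of 2 to 4 points in the planned limits is small beside that.

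**Completers.** With exactly three withdrawals among eight, five remain:

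| Non-safety | Safety | More than 2 non-safety? | Completers without replacement |
|---|---|---|---|
| 3 | 0 | yes, replace | not applicable |
| 2 | 1 | no | 5 |
| 1 | 2 | no | 5 |
| 0 | 3 | no | 5 |

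So the literal gap exists. The documents give no withdrawal rate, so I attach no probability to it.

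**Completers and evaluable subjects.** These counts differ in both directions. A completer can lose AUC-infinity under SAP 7.1. A subject who leaves early can still contribute: Table 1 of the protocol gives a latest tmax of 9.50 h for DRV and 5.02 h for COBI, and mean half-lives of 6.7 h and 3.8 h, against 72 h of sampling. Five completers therefore need not mean n=5 for every parameter. SAP 7.1 has N displayed as the number of subjects for whom a parameter was calculated, so readers will see the actual count.

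**The case for a change.** The best case for a change runs as follows. The sponsor chose to justify the study at n=6, so the better result at 7 or 8 does not rescue the sentence as written. A planning CV below an observed value for one of the parameters it covers deserves a reason. The mismatch over completers is a matter of text and needs no assumed rate. At five subjects the range widens to 69.3% to 144.4% at a CV of 40%, or 67.0% to 149.3% at 44%. Protocol 10.2 also makes vomiting within 6 hours an automatic withdrawal without saying whether it counts as a safety reason, so the trigger itself can be unclear. And the correction would be only a few words.

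Much of this is true as description. At n=6 the range is slightly narrow for one COBI parameter, and six completers are not assured. What does not stand is the step to a needed change. Both maxima and the planning value are printed side by side, so nothing is hidden and any reader can rescale. The sentence about eight subjects explains why eight rather than six are enrolled, and Protocol 4 and the synopsis state the safety exception immediately after it. Restating evaluability in the sample size section would only point to rules already in Protocol 11.3 and SAP 2.3.2 and 7.1. A few words in the protocol also require a formal amendment under Protocol 17.1.

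**Conclusion.** No change to the plan. The 73% to 137% range is exact for its disclosed assumptions, a CV of about 40% and six evaluable subjects. Using one rounded CV rather than one per analyte is a choice of presentation: conservative for DRV, and optimistic by about 2 and 4 points only for the most variable COBI parameter. That shortfall disappears if at least seven of the eight enrolled subjects are evaluable.

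The wording on six completers is an aim with a visible exception. Three withdrawals, at least one of them for safety, can leave five of eight; how likely that is cannot be judged from the documents.

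Neither point bears on a result. There is no hypothesis test, margin or precision criterion, and SAP 2.5 reports 90% confidence intervals of the geometric mean from the observed data. Different wording would leave enrolment, procedures, analyses and conclusions as they are. The conclusion rests on log-normal parameters and on the CVs cited from the earlier study; the individual COBI CVs below the maximum are not given.
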